## **2. Objectives**

### **2.1 Primary Objective**

- To assess the safety and tolerability of rovalpituzumab tesirine in subjects with specific delta-like protein 3 (DLL3)-expressing advanced solid tumors.

### **2.2 Secondary Objectives**

- To explore the antitumor activity of rovalpituzumab tesirine in subjects with specific DLL3-expressing advanced solid tumors.
- To study the pharmacokinetics (PK) of and incidence of anti-therapeutic antibodies (ATA) against rovalpituzumab tesirine in subjects with specific DLL3-expressing advanced solid tumors.

### **2.3 Exploratory Objectives**

- To explore the expression of DLL3 in specific delta-like protein 3-expressing advanced solid tumors, and its relationship to clinical outcome during treatment with rovalpituzumab tesirine.
- To explore the effect of rovalpituzumab tesirine on disease biomarkers and pharmacodynamics.
- To assess change in patient reported outcomes (PRO) within the expansion cohorts (Part B) utilizing the European Organization for Research and Treatment of Cancer (EORTC) Quality of Life Questionnaire-Core 30 (QLQ-C30) questionnaire and EuroQoL Five Dimension Questionnaire (EQ-5D-5L) during treatment with rovalpituzumab tesirine.

## **2.4 Endpoints**

### **2.4.1 Safety Endpoints**

- Adverse events (AEs)
- Vital signs
- Physical examination
- Body weight
- Laboratory abnormalities
- Electrocardiographic parameters (e.g., QT interval corrected for heart rate [QTc], QT interval corrected for heart rate by Fridericia's formula [QTcF])
- ECHO
- Components of a fluid retention questionnaire

### 2.4.2 Efficacy Endpoints

- Response assessments according to Response Evaluation Criteria in Solid Tumors (RECIST v1.1) (Eisenhauer 2009), including ORR and CBR
- DOR
- PFS
- PFS status after 6 months from the initiation of study treatment
- OS
- Prostate cancer only:
  - Response assessments according to Prostate Cancer Clinical Trials Working Group 3 (PCWG3), including prostate-specific antigen (PSA) response rate, DOR, and radiographic PFS
  - Circulating tumor cell (CTC) conversion rate (e.g.,  $\geq 5$  CTCs/7.5 mL to  $< 5$  CTCs/7.5 mL)
- GBM only:  
GBM will be assessed using Response Assessment in Neuro-Oncology (RANO) criteria. (Appendix 13.3.4)

### 2.4.3 Patient Reported Outcomes Endpoint

- Change in PROs (based on the EORTC QLQ-C30 and EQ-5D-5L questionnaires)

### 2.4.4 Pharmacokinetics, Biomarker, and Pharmacodynamic Endpoints

- Specific PK parameters of rovalpituzumab tesirine (e.g., maximum concentration [ $C_{max}$ ], area under the curve [AUC])
- ATA against rovalpituzumab tesirine
- Tumor DLL3 expression
- Inflammatory markers (locally tested)
- Blood tumor markers
- Biomarkers, including soluble DLL3
- CTCs

### 3. Investigational Plan

#### 3.1 Summary of Study Design

This is a multicenter, open-label study of rovalpituzumab tesirine in subjects with DLL3-expressing advanced solid tumors. The study will include 7 cohorts of subjects with the following cancers:

1. Malignant melanoma
2. Medullary thyroid cancer (MTC)
3. Glioblastoma
4. Large cell neuroendocrine carcinoma (LCNEC) of any origin
5. Neuroendocrine prostate cancer (NEPC)
6. High-grade gastroenteropancreatic neuroendocrine carcinoma (GEP NEC)
7. Other neuroendocrine carcinoma (NEC) and high grade neuroendocrine tumors (NET)
8. Solid tumors other than the above

As of protocol version 4.0, cohort 3 (Glioblastoma) is closed to enrollment. Specific guidance for cohort 3 (Glioblastoma) subjects (protocol version 3.0) are provided in Appendix 13.3.

Each disease-specific cohort will include two parts:

- Part A – Dose-Regimen Finding: Will involve disease-specific dose escalation, and possible dose-interval modification, to define the maximum tolerated dose (MTD) and/or possible recommended Phase 2 dose(s) (RP2Ds).
- Part B – Expansion Cohorts: Disease-specific expansion cohorts may be enrolled. Subjects in the expansion cohorts will be treated with a dose regimen(s) at or below the MTD and/or RP2D determined in Part A.

Dose limiting toxicities (DLTs) will be assessed during the DLT Evaluation Period (Section 3.1.3) for subjects in Part A, the dose regimen finding portion of the trial.

Safety will be monitored throughout the trial by the Safety Monitoring Committee (SMC) consisting at least of a Medical Monitor, Investigators, and the study biostatistician. The SMC will meet routinely to review the emerging safety, select pharmacodynamic and efficacy data, and may make dose-escalation and dosing-interval recommendations. The SMC may recommend further evaluation of safety at a given dose level, investigation of alternative dose regimens, including a dose level that is intermediate to the planned dose levels, modification of the dosing interval, limitation to the maximum number of doses, and/or elimination or cancellation of a dose level(s) in a cohort based on the experience in other cohorts. The SMC will also review cumulative safety data in order to identify safety concerns that may emerge due to cumulative exposure beyond the DLT window. The process for dose-escalation decisions and dose-interval recommendations, and the roles and responsibilities of the SMC may be detailed separately.

Tumor response will be assessed every 6 weeks during active study treatment until 24 weeks, and then every 12 weeks thereafter. Treatment decisions by the Investigator will be based on RECIST v1.1 (and/or PCWG3 for prostate cancer; [Appendix 13.7](#)).

Subjects will be eligible to continue treatment until unacceptable toxicity, disease progression (PD), withdrawal of consent, study termination, or completion of a planned course of treatment (if a regimen with a limited number of doses is selected), whichever occurs first. Subjects who discontinue study treatment prior to PD will be evaluated for response every 6 weeks until 24 weeks, then every 12 weeks until PD or initiation of new anticancer treatment, whichever occurs first, and will afterwards be followed for survival until death or study termination, whichever occurs first. [Appendix 13.7](#) includes specific additional guidance for prostate cancer subjects.

Blood samples for PK, immunogenicity, biomarker and pharmacodynamics assessments will be collected at protocol-defined time points to support the study endpoints ([Sections 7.4](#) and [7.5](#)).

### 3.1.1 Part A Dose-Regimen Finding

[figure not shown]
For Part A, the planned dose levels of rovalpituzumab tesirine are presented in [Table 3-1](#). Initially, rovalpituzumab tesirine will be administered according to the Schedule Q6wk, on Day 1 of each 6-week cycle, continuous dosing. If the MTD is determined to be 0.3 mg/kg in the initial 3 dose levels, further dose escalation will be stopped.

**Table 3-1 Planned Dose Levels in Part A**

Dose Level	Dose Level Schedule Q6wk (every 6 weeks)
1	0.2 mg/kg
2	0.3 mg/kg
3	0.4 mg/kg

A standard 3+3 dose-escalation approach will be utilized ([Figure 3-1](#)). Subjects will be enrolled in groups of 3.

**Figure 3-1 Dose-Escalation Decision Summary**

During 3+3 dose escalation, DLTs will be assessed during the DLT Evaluation Period (Section 3.1.3). If 0 of 3 subjects experience a DLT in a cohort, the next dose level will be opened for enrollment. If  $\geq 2$  of 3 subjects in a cohort experience a DLT, the MTD will have been exceeded and dose escalation will stop. If 1 of 3 subjects in a cohort experiences a DLT, an additional 3 subjects will be treated at that same dose level for a total of 6 subjects. If none of the 3 additional subjects experiences a DLT (1 of 6 subjects with a DLT), dose escalation will continue to the next higher dose level. If 1 or more of the 3 additional subjects experiences a DLT ( $\geq 2$  of 6 subjects with a DLT), the MTD will have been exceeded and dose escalation will not continue. Subjects who do not complete the DLT-evaluation period due to non-DLT reasons will not be considered DLT-evaluable and will be replaced for the DLT evaluation.

The MTD and RP2D will be determined by the Sponsor in consultation with the SMC after a review of all available data. At least 6 subjects must be treated at the putative MTD or RP2D, with no more than 1 incident of DLT.

If 3 or more disease-specific cohorts clear the 0.3 mg/kg or 0.4 mg/kg dose level and the Q6wk schedule, then the SMC may evaluate all the data available to determine an appropriate RP2D and the Part B expansion may proceed for all the cohorts in the study at these dose(s) and schedule.

During dose escalation, additional subjects may be enrolled at a dose level previously declared to be tolerated in order to explore further the safety and tolerability of the regimen. For instance, if

all 3 or 6 subjects necessary for DLT evaluation have been enrolled in a cohort, but have not yet completed the DLT evaluation period, additional subjects may be enrolled at a lower dose level(s), with approval of the Medical Monitor and Sponsor.

### 3.1.2 Part B Expansion Cohorts

To explore the recommended dosing regimen for distinct disease subsets, subjects will be enrolled in disease-specific expansion cohorts in Part B. The dose regimen(s) to be examined in the disease-specific cohorts will be the MTD determined in Part A or a lower dose(s) and/or regimen(s), depending on the cumulative data. For example, a lower dose regimen may consist of a finite number of doses and/or a mixed-dose regimen, with all doses at or below MTD, but varying based on the cycle. The dose(s), regimen(s) and schedule(s) for each expansion cohort will be determined by the Sponsor in consultation with the SMC. For Part B, approximately 174 subjects may be enrolled. The “Other NEC/NET” and “Other Solid Tumor” cohorts will each enroll 30 subjects. Additional information regarding sample size is provided in [Section 10.1](#), Determination of Sample Size.

### 3.1.3 Definition of Dose-Limiting Toxicities

The DLT evaluation period is the first 3 weeks of the first cycle of treatment for all subjects in Part A. DLTs are defined as any of the following in the DLT evaluation period, graded according to the National Cancer Institute’s Common Terminology Criteria for Adverse Events (NCI CTCAE), version 4.03:

- Grade 4 thrombocytopenia (or Grade 3 thrombocytopenia with bleeding) lasting more than 7 days and/or requiring platelet transfusion
- Grade 4 neutropenia lasting more than 7 days, and/or requiring hematopoietic growth factor rescue, or any febrile neutropenia (Grade 3 or 4 neutropenia with concurrent fever  $\geq 38.3^{\circ}\text{C}$ )
- Grade 4 anemia unrelated to underlying disease
- Clinically-significant Grade 3 or 4 non-hematologic laboratory abnormality that does not resolve to Grade 0/1 or baseline within 7 days
- Grade 3 or 4 non-laboratory AE with the exception of fatigue, asthenia, nausea, or other manageable constitutional symptom

The following events will not be considered DLTs:

- Any AE  $\geq$  Grade 3 clearly determined to be unrelated to study drug (e.g., PD)
- $\geq$ Grade 3 isolated alkaline phosphatase, amylase or lipase laboratory abnormality of any duration

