
 
• Grade 3 serosal effusions (pleural effusions, pericardial effusions, and ascites) and edema
 
• Grade 2 capillary syndrome
 
• Grade 4 thrombocytopenia/ Grade 3 thrombocytopenia with bleeding/ Need for platelet transfusion
 
• Grade 4 febrile neutropenia
 
• Grade 4 (<math>>20.0 \times \text{ULN}</math>) ALT or AST or Grade 3 (<math>>5.0\text{--}20.0 \times \text{ULN}</math>) ALT or AST elevation with concomitant total bilirubin Grade 2 or higher (<math>>1.5 \text{ULN}</math>)
 
• Grade 3 or higher hypoalbuminemia (<math><2 \text{g/dL}</math>)
 
• Grade 2 pneumonitis
 
	

Toxicities Requiring Discontinuation of Investigational Product at First Occurrence

• Grade 4 photosensitivity or skin reaction (Section 5.5.2)

• Drug induced liver injury is confirmed (refer to Section 5.5.3 for definition)

• Life threatening Infusion related reaction or hypersensitivity

• Grade <math>\geq 3</math> pneumonitis

Abbreviations: ALT = alanine aminotransferase; ANC = absolute neutrophil count; AST = aspartate aminotransferase; DILI = drug induced liver injury; INR = International normalized ratio; ULN = upper limit of normal.

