### 5.5.3 Potential Drug-Induced Liver Injury

Wherever possible, timely confirmation of initial liver-related laboratory abnormalities should occur prior to the reporting of a potential drug-induced liver injury (DILI) event. All occurrences of potential DILIs, meeting the defined criteria, must be reported as SAEs.

Potential drug-induced liver injury is defined as:

- ALT or AST elevation  $>3\times$  ULN; *and*
- Concurrent total bilirubin  $>2\times$  ULN, without initial findings of cholestasis (elevated serum alkaline phosphatase), *and*
- No other immediately apparent possible causes of aminotransferase (AT) elevation and hyperbilirubinemia, including, but not limited to, viral hepatitis, pre-existing chronic or acute liver disease or tumor(s), or the administration of other drug(s) known to be hepatotoxic

In general, an increase of AT to  $>3\times$  ULN should be followed by repeat testing within 48–72 hours of all four of the usual measures (ALT, AST, alkaline phosphatase, total bilirubin) to confirm the abnormalities and to determine if they are increasing or decreasing. Inquiry regarding symptoms should also be made (e.g., fatigue, nausea, vomiting, right upper quadrant pain or tenderness, fever, rash). Subjects may be retested locally, but normal laboratory ranges should be recorded and results made to the Investigator immediately. All data must be recorded in the CRF. If symptoms persist or repeat testing shows AT  $>3\times$  ULN for subjects with normal baseline measures or 2-fold increases above baseline values for subjects with elevated values before drug exposure, close observation should be initiated. If close monitoring is not possible, study drug should be discontinued.

Close observation includes:

- Repeating liver enzyme and serum bilirubin tests 2 or 3 times weekly. Frequency of retesting can decrease to once a week or less if abnormalities stabilize or the trial drug has been discontinued and the subject is asymptomatic.
- Obtaining a more detailed history of symptoms and prior or concurrent diseases
- Obtaining a history of concomitant drug use (including nonprescription medications and herbal and dietary supplement preparations), alcohol use, recreational drug use, and special diets
- Ruling out acute viral hepatitis types A, B, C, D, and E; autoimmune or alcoholic hepatitis; non-alcoholic steatohepatitis (NASH); hypoxic/ischemic hepatopathy; and biliary tract disease

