- Obtaining a history of exposure to environmental chemical agents
- Obtaining additional tests to evaluate liver function, as appropriate (e.g., international normalized ratio [INR], direct bilirubin)
- Considering gastroenterology or hepatology consultations

Discontinuation of study drug should be considered if potential DILI is suspected and:

- ALT or AST  $>8\times$  ULN
- ALT or AST  $>5\times$  ULN for more than 2 weeks

- ALT or AST  $>3\times$  ULN and (TBL  $>2\times$  ULN or INR  $>1.5$ )
- ALT or AST  $>3\times$  ULN with the appearance of fatigue, nausea, vomiting, right upper quadrant pain or tenderness, fever, rash, and/or eosinophilia

All subjects showing possible DILI should be followed until all abnormalities return to normal or to the baseline state.

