### 8.1 Medical Complaints

The Investigator will monitor each subject for clinical and laboratory evidence of AEs on a routine basis throughout the study. The Investigator will assess and record any AE in detail, including the date of onset, event diagnosis (if known) or sign/symptom, severity, time course (end date, ongoing, intermittent), relationship of the AE to study drugs, and any action(s) taken. For SAEs considered as having "no reasonable possibility" of being associated with study drugs, the Investigator will provide another cause of the event. For AEs to be considered intermittent, the events must be of similar nature and severity. AEs, whether in response to a query, observed by site personnel, or reported spontaneously by the subject will be recorded.

All AEs will be followed to a satisfactory conclusion.

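### The DLT list has no criterion for drug-induced liver injury, so a confirmed case that Table 5-1 lists for discontinuation can go uncounted in the 3+3 rule; the effect is probably small and the fix is cheap.

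*Combined protocol and SAP*

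**What the plan says.** **DLT list (Section 3.1.3).** The window is the first 3 weeks of Cycle 1 in Part A. There are three hematologic criteria and two others. One is "Clinically-significant Grade 3 or 4 non-hematologic laboratory abnormality that does not resolve to Grade 0/1 or baseline within 7 days". The other is a Grade 3 or 4 non-laboratory adverse event, with exceptions for constitutional symptoms. None names DILI or combines aminotransferases with bilirubin.

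**Liver rules (Section 5.5.3).** Potential DILI is ALT or AST above 3×ULN with concurrent total bilirubin above 2×ULN, no initial cholestasis, and no other immediately apparent cause. "All occurrences of potential DILIs, meeting the defined criteria, must be reported as SAEs". An aminotransferase rise above 3×ULN "should be followed by repeat testing within 48–72 hours", and a work-up for other causes is described. At the potential stage stopping is optional: "Discontinuation of study drug should be considered if potential DILI is suspected", if one of four listed conditions is also met.

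**Dose modification (Table 5-1).** Under "Toxicities Requiring Discontinuation of Investigational Product at First Occurrence" the table includes the row "Drug induced liver injury is confirmed", referring to Section 5.5.3 for the definition. It prints Grade 3 ALT/AST as above 5 to 20×ULN and bilirubin of Grade 2 or higher as above 1.5×ULN. Sections 5.2.4 and 5.2.4.3 allow adjustment on the investigator's judgment with Medical Monitor approval.

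**Escalation (Section 3.1.1).** 0/3 DLTs opens the next dose; 1/3 adds three subjects; 1/6 escalates; 2 or more of 3, or of 6, stops. The MTD or RP2D needs at least 6 treated subjects with no more than one DLT.

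**The concern.** The laboratory criterion requires three things at once: clinical significance, Grade 3/4, and persistence beyond 7 days. The DILI definition requires neither Grade 3 nor persistence. A confirmed drug-caused liver injury can therefore be serious enough to be listed for stopping the drug at its first occurrence and yet leave the subject recorded as DLT-free.

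The DLT count drives the written escalation rule. One uncounted case can turn 1/3 (expand) into 0/3 (escalate), or 2/6 (stop) into 1/6 (escalate). It is also left out of the check of at least 6 subjects with no more than one DLT. Under Section 3.1.1, if three or more disease cohorts clear 0.3 or 0.4 mg/kg, the SMC may set an RP2D and Part B may open for all cohorts, so a miscount in one cohort could inform the dose used in others.

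**Working it through.** **1. Setting the definitions side by side.** The inputs are the Section 5.5.3 thresholds (ALT/AST >3×ULN, bilirubin >2×ULN), Grade 3 ALT/AST (>5×ULN) from Table 5-1, and the 7-day condition in Section 3.1.3. In these examples bilirubin is 2.5×ULN.

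| ALT (×ULN) | Duration | Meets DILI laboratory thresholds | Laboratory DLT |
|---|---|---|---|
| 4 | 14 days | yes | no |
| 5 | 30 days | yes | no |
| 8 | resolves in 6 days | yes | no |
| 25 | resolves in 7 days | yes | no |
| 8 | 8 days | yes | yes, if clinically significant |

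This gives two uncounted patterns:

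- (a) ALT/AST above 3 and up to 5×ULN, with bilirubin above 2×ULN but below Grade 3.
- (b) Grade 3/4 values that return to Grade 0/1 or baseline within 7 days.

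Pattern (a) needs a Grade 3 bilirubin limit, which the documents do not print. I assume >3×ULN, so the affected bilirubin band is above 2 and up to 3×ULN. A limit between 2 and 3×ULN narrows the band, and a limit at or below 2×ULN empties it. Pattern (b) does not depend on that limit.

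**2. The other route into the count.** Section 8.1 asks the site to record "event diagnosis (if known) or sign/symptom, severity", and Section 8.1.2 gives a fallback severity scale. A site could enter a liver diagnosis and grade it 3/4, which would meet the non-laboratory criterion. The protocol does not say whether DILI is a laboratory or a non-laboratory event, and SAE status does not set a grade. The route is open but not assured.

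**3. Size under the 3+3 rule.** The protocol states no operating characteristics, so there is no figure to reproduce. With per-subject DLT probability p,

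P(escalate) = (1−p)³ + 3p(1−p)² × (1−p)³ = (1−p)³ + 3p(1−p)⁵.

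The following are assumptions, not figures from the documents:

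- b: the rate of all DLTs counted as written.
- d: the rate of confirmed DILI of pattern (a) or (b) in the 3-week window.
- r: the share of those already captured as a Grade 3/4 diagnosis.
- q = d(1−r): the uncaptured rate, independent of other DLTs.

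As written, p = b. If the uncaptured cases counted, p = 1 − (1−b)(1−q).

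Worked case, b = 0.10 and q = 0.01:

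- As written: 0.9³ + 3(0.1)(0.9)⁵ = 0.7290 + 0.1771 = 0.9061.
- If counted: p = 1 − 0.90 × 0.99 = 0.109, so 0.7073 + 0.1836 = 0.8910 (rounded).
- Difference: 1.5 percentage points.

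| q | b = 0.10: written → counted | Difference (points) | b = 0.20: written → counted | Difference (points) |
|---|---|---|---|---|
| 0.25% | 0.9061 → 0.9024 | 0.37 | 0.7086 → 0.7043 | 0.43 |
| 0.5% | 0.9061 → 0.8987 | 0.75 | 0.7086 → 0.6999 | 0.87 |
| 1% | 0.9061 → 0.8910 | 1.52 | 0.7086 → 0.6912 | 1.74 |
| 2% | 0.9061 → 0.8751 | 3.11 | 0.7086 → 0.6738 | 3.48 |

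With r = 50%, d = 1% gives q = 0.5%. With r = 100% the difference is zero. Over b from 0 to 0.60, the largest difference is 0.87 points at q = 0.5%, 1.75 at 1% and 3.52 at 2%, reached at b of about 0.17 to 0.18.

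**The case against.** The strongest reply is that this rarely matters and is largely covered.

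- **Rarity.** Section 1.4 names bone marrow, lung and kidney as the toxicology targets, not liver. The adverse events listed in Sections 1.2 and 1.4 include no liver event, although those lists are mostly of frequent terms and cannot exclude rare DILI. Section 5.5.3 excludes cases with cholestasis, existing liver disease or tumor, or other hepatotoxic drugs. The remaining cases must start within 3 weeks and fit pattern (a) or (b).
- **Other safeguards.** Potential DILI is an SAE, reportable within 24 hours. The SMC can ask for more evaluation at a dose or cancel a dose level, and the MTD/RP2D is set on all available data. Table 3-1 stops at 0.4 mg/kg every 6 weeks; the earlier Phase 1 MTD was 0.4 mg/kg every 3 weeks (Section 3.2.3), and up to 0.8 mg/kg every 3 weeks has been given (Section 1.4).
- **Different purposes.** DLT lists steer escalation and stopping rules protect individuals, so the two need not match.

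Most of this stands and limits the size of the point. It does not remove it: SMC discretion and SAE reporting leave the written count unchanged.

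A reader might infer four stronger things that the documents do not support.

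- *Subjects are unprotected from liver injury.* Table 5-1 and Section 5.5.3 apply whatever the DLT status.
- *The two lists must agree throughout.* Table 5-1 itself uses the 7-day condition for other laboratory events. DILI stands out because the other three discontinuation rows are non-laboratory events that, at Grade 3 or 4 and not clearly unrelated to drug, meet the DLT criterion.
- *Stopping is absolute.* It can be adjusted with Medical Monitor approval, and for potential DILI it need only be considered.
- *Confirmation is wholly undefined.* Section 5.5.3 describes a repeat test and a work-up; it does not say what result makes a case confirmed.

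**Conclusion.** The gap is real on the text. A confirmed DILI of pattern (a) or (b) is not a laboratory DLT, and nothing ensures that it enters the count as a non-laboratory one. Pattern (a) rests on the assumed Grade 3 bilirubin limit; pattern (b) does not.

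The effect is probably small and cannot be quantified from the documents, because the rates of DILI, of other DLTs and of capture as a diagnosis are all assumed. For uncaptured rates of 0.5% to 2%, the written rule escalates more often than it would with these cases counted, by at most about 0.9 to 3.5 points per dose level. That does not support a reading that escalation in this trial is materially unsafe. It supports a low-priority correction, worth making because a serious drug-related event should not be miscounted when the rule is followed exactly.

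**What to change.** Add one bullet to the DLT list in Section 3.1.3: *drug-induced liver injury meeting the Section 5.5.3 definition with onset in the DLT evaluation period, still meeting it on the 48–72 hour repeat test and with no other cause found, regardless of individual laboratory grade or duration.* This also states what counts as confirmed for DLT purposes. The repeat test should be judged against the DILI thresholds themselves. The "2-fold increases above baseline values for subjects with elevated values before drug exposure" in Section 5.5.3 is a trigger for close observation, not part of the DILI definition, and should not be used here.

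Apply the bullet to dose levels still under evaluation, and have the SMC consider potential-DILI SAEs already reported when setting the RP2D. The documents do not show how many dose levels remain open, so the look-back may be the more useful part.

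The cost is one bullet and a review of reports already collected, with no new visits or tests. The downside is that a dose level may be expanded or stopped slightly more often, and an escalation decision may wait briefly for the work-up of a suspected case.
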